### Dose Modification

#### Lipid Intolerance

If lipid intolerance develops, defined as serum triglyceride levels > 200 mg/dL, the following will be considered prior to reducing the dose:

- a) If the level was obtained while the patient was receiving a continuous 24-hour infusion of Omegaven®, the total dose should be infused over 20 hours, and a repeat serum triglyceride level obtained prior to resuming the infusion 4 hours later.
- b) Other sources of lipid intolerance should be considered and addressed (drugs, renal disease)

If the triglycerides continue to remain high despite the aforementioned interventions, a dosage reduction of 25% of the current dose will be considered.

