#### **G. Adverse Event Criteria and Reporting Procedures**

Adverse events (AEs) will be assessed and reported from the time of the first Omegaven® infusion until exit from the study in accordance with UNMC Pediatric IRB reporting requirements. In particular, the patient will be observed during and shortly after Omegaven® administration for the occurrence of anaphylactic or allergic reactions. Other expected adverse events include death, blood stream infection; transfer to ICU for treatment of respiratory distress or hemodynamic instability; re-hospitalization for treatment of blood stream infection, dehydration, electrolyte abnormalities, catheter malfunctions, bowel obstructions, and urinary tract infection. Unexpected adverse events will also be assessed and reported in compliance with the UNMC Pediatric IRB requirements. Patients experiencing any adverse events that are moderate or severe in nature and that may be related to Omegaven® will have their treatment temporarily halted until the adverse event has resolved. Dose modifications will occur as described above. If a dose reduction is made for adverse events later considered to be unrelated to Omegaven®, the Omegaven® dose will be increased back to the dose prescribed prior to the dose reduction. Patients with anaphylactic or allergic reactions will not continue Omegaven® treatment.

Any serious or unsuspected adverse events will be reported to the IRB and the FDA within 72 hours of the occurrence being known, or immediately if the event is fatal or life threatening as per UNMC Pediatric IRB Policy on Adverse and Unexpected Events and Unanticipated Risks to Research Subjects and Others. This will be done in person, by telephone, or email, and by completion of the IRB's form for adverse/unexpected event reporting.

Adverse events are detected by Children's Hospital & Medical Center acute care medical and nursing staff during provision of standard care services including the routine monitoring of vital signs and daily physical exam data. Adverse events identified by Children's Hospital & Medical Center staff are reported to the Principal Investigator immediately by telephone or pager, and subsequently to the appropriate board or committee.

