**Patients will be withdrawn from the study for any of the following:**

- a) Toxicity considered unacceptable by the Principal Investigator (i.e. Evidence of burr cell anemia (reported toxicity); Continued lipid intolerance (triglyceride >200) despite dose reduction attempts and administration modification; evidence of coagulopathy (INR > 2.0)).
- b) Patient/guardian requests to discontinue treatment and/or observation for any reason.
- c) A suitable organ has been located and the patient is able to undergo a liver or liver/intestinal transplant.
- d) Decision by the Principal Investigator that termination is in the patient's best medical interest.
- e) Patient is lost to follow up.

In the event that a patient is withdrawn from the protocol, study staff will document the date of withdrawal, the reason for withdrawal, and the results of all measurements of interest made up to date of withdrawal.

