#### **Safety Labs Schedule:**

Lab Name	Schedule*
Serum triglycerides	At baseline, weekly for 4 weeks, monthly thereafter
Coagulation labs	At baseline, weekly until direct bilirubin is < 2mg/dL, monthly thereafter
Fatty acid profile	At baseline, monthly thereafter

\*minimum requirements, may be performed more frequently for routine clinical care

If under the discretion of the principal investigator the patient is able to return home and receive Omegaven®, the patient is required to return to Children's Hospital & Medical Center every 2 months or other mutually agreed upon schedule for evaluation and follow up. The Principle Investigator also requires for arrangements to be made through the patient's home health care agency for the required weekly or monthly blood draws the patient will need while at home in order to remain on Omegaven®. The lab results then must be faxed to Children's Hospital & Medical Center in a timely manner. Additionally, measures will be taken to decrease the chance of administration errors when Omegaven® is given in the home. Families will be provided with a letter outlining strategies for reducing medication administration errors, such as independent double-checks.

Dose reduction will occur if there is evidence of lipid intolerance (serum triglycerides  $>$  200mg/dL) or evidence of bleeding. Growth indices include weight, length, and head circumference will also be monitored.

Other standard care laboratory results will be captured for the Omegaven® protocol. These are listed along with the standard schedule in Table 3.

The frequency of laboratory monitoring may be reduced to monthly or as clinically necessary, for patients who have been on a stable regimen of Omegaven® for a minimum of 4 months and whose serum bilirubin and hepatic enzymes have normalized.

The study team will round on all inpatients receiving Omegaven® therapy. A complete comprehensive case review for all inpatients receiving Omegaven® therapy under the compassionate-use protocol and any outpatients issues will be discussed among [name], [name], and the study coordinator. All pertinent medical, nutritional, and psychosocial outpatient information will be reviewed during these case reviews.

[name], Department of Surgery, Children's Hospital & Medical Center  
[name], Department of Surgery, Children's Hospital & Medical Center  
[name], Pediatric Research Office, Dept. of Pediatrics, UNMC  

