**Overdose:**

In the event of an overdose of Omegaven®, there is a risk of developing fat overload syndrome that may occur when the triglyceride level rises  $>200$  mg/dL acutely as a result of too rapid a rate of infusion, or chronically at high infusion rates in associated with a change in the patient's clinical condition (e.g., renal dysfunction, sepsis). In such cases, the infusion should be stopped or, if necessary, continued at a reduced dose. Metabolic acidosis has occurred in patients receiving Omegaven® at excessive doses without simultaneous administration of dextrose.

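### At triglycerides > 200 mg/dL the protocol gives two incompatible dose instructions, and its bleeding instructions leave precedence unclear behind a cross-reference that leads nowhere

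*Protocol*

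**What the plan says.** **Triglycerides.** The Dose Modification section, under Lipid Intolerance, reads: "If lipid intolerance develops, defined as serum triglyceride levels > 200 mg/dL, the following will be considered prior to reducing the dose". The measures are a change to the infusion schedule with a repeat level, for a child on a continuous 24-hour infusion, and a search for other causes. If levels stay high after that, "a dosage reduction of 25% of the current dose will be considered". The Safety Labs Schedule, in the Data and Safety Monitoring Plan, uses the same 200 mg/dL limit and says: "Dose reduction will occur if there is evidence of lipid intolerance".

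**Bleeding.** The same Safety Labs sentence adds a second trigger, "or evidence of bleeding", without a grade. Section G (Adverse Event Criteria and Reporting Procedures) says that patients with moderate or severe events that may be related to the product "will have their treatment temporarily halted until the adverse event has resolved". It continues: "Dose modifications will occur as described above".

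**Related text.** The withdrawal list gives, as an example of toxicity that the investigator judges unacceptable, "Continued lipid intolerance (triglyceride >200) despite dose reduction attempts and administration modification". INR above 2.0 is another example in the same item. The Overdose text, on fat overload syndrome, says that "the infusion should be stopped or, if necessary, continued at a reduced dose".

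**The concern.** These are operating instructions for an investigational product given to children. According to the Data and Safety Monitoring Plan, both attending staff and the investigators evaluate the safety labs, and results for home patients arrive by fax. Several people may therefore act on the same laboratory value. If one follows the Dose Modification section and another the Safety Labs Schedule, two children with the same result receive different doses, and both are treated according to protocol.

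There is a smaller analytic consequence. The dose received, and whether a child ever reaches the withdrawal criterion that presupposes attempts at dose reduction, then depend partly on which section was read.

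**Working it through.** The protocol states no figure to reproduce. The check sets the instructions side by side, one trigger at a time.

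**Trigger 1: first triglyceride value above 200 mg/dL**

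- Dose Modification: other measures come before reduction. Reduction follows only if levels stay high, is discretionary, and its size is 25% of the current dose.
- Safety Labs Schedule: reduction is mandatory. It gives no prior step, no size and no reference to Dose Modification.

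An illustration uses the protocol's own numbers: the goal dose of 1 g/kg/day from Details of Omegaven Administration, given over 24 hours.

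- Under Dose Modification the full daily dose is kept and given over 20 hours: 1 ÷ 20 = 0.05 g/kg/hour, with the daily total unchanged at 1 g/kg.
- Under the Safety Labs Schedule the daily dose falls at once by an unstated amount. If the 25% from Dose Modification is assumed, it becomes 1 × (1 − 0.25) = 0.75 g/kg/day.

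The daily dose is either unchanged or lower, so both instructions cannot be followed. The illustration shows divergence only and says nothing about which instruction is right.

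**Trigger 2: bleeding**

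- Safety Labs Schedule: reduce, at any grade.
- Section G: halt temporarily if the event is moderate or severe and may be related.
- A mild or clearly unrelated bleed meets only the first rule. A moderate bleed that may be related meets both, and the protocol does not say which comes first or whether reduction applies on resumption.
- Section G's pointer to dose modifications described above leads to the Dose Modification section, which covers lipid intolerance only. The one bleeding rule appears later, in the Safety Labs Schedule. Section G also describes restoring a dose that was reduced for an adverse event, so it presupposes a reduction rule that the referenced section does not contain.

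**Effect on outcomes**

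- Primary safety outcomes (Analysis of Safety and Tolerability): whether the triene/tetraene ratio was ever above 0.2 and whether INR was ever above 2, analysed descriptively. Once an INR above 2 is recorded in the analysis window, later withdrawal cannot remove it.
- Secondary measures (Outcome/Endpoints): maximum triglyceride can be shifted by how soon someone acts at 200 mg/dL. Days with INR above 2 over follow-up time can be cut short by withdrawal.
- The Data Analysis Plan treats a patient as receiving Omegaven despite temporary discontinuation. It does not mention permanent withdrawal.

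**The case against.** **The Safety Labs sentence may be shorthand.** It could be a summary of the Dose Modification section. That is possible, but it contains no cross-reference, and its mandatory wording does not summarise a discretionary step that comes after other measures. A reader who meets only the monitoring plan would not know of the earlier section.

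**Halting and reducing can partly be read together.** The halt is temporary and limited to moderate or severe events that may be related. Reduction could apply to milder bleeding or to the dose on resumption. This stands: the bleeding text is not a flat contradiction. What remains is the missing precedence where both rules apply, and the empty cross-reference.

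**Stronger readings that the protocol does not support.**

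- A reader might infer that one finding attracts five competing responses: consider reduction, reduce, stop, halt or withdraw. That count merges different triggers. The Overdose text concerns fat overload from too rapid an infusion or chronically high infusion rates, not every value above 200 mg/dL at the protocol dose.
- Withdrawal for triglycerides is worded as a later step, after attempts at reduction.
- INR above 2.0 is a laboratory value and differs from clinical bleeding. Its place in the withdrawal list is qualified by the investigator's judgement.
- A reader might also infer that withdrawal ends data collection and so damages the primary safety results. The withdrawal section records measurements up to the date of withdrawal. Discontinuation of Therapy provides at least two months of follow-up after treatment stops. Together they leave the matter open, and the primary safety outcomes are descriptive and of the ever-occurred type.

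**Monthly case review.** The investigators review all treated patients at least monthly. This limits uncoordinated decisions but does not remove the conflict in wording.

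**Conclusion.** The point holds. The protocol contains one clear contradiction, between Dose Modification and the Safety Labs Schedule at triglycerides > 200 mg/dL. It also contains one unresolved overlap, on bleeding, with a cross-reference to a section that has no bleeding rule. The Overdose text and the withdrawal list are not direct contradictions, but they need to agree with whatever rule results.

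The main consequence is inconsistent handling of the same value, which bears on safety and on the dose received. For outcomes, the effect is limited to secondary measures such as maximum triglyceride and days with INR above 2 over follow-up. The protocol gives no expected frequency of high triglycerides or bleeding, so the share of children affected cannot be estimated. The conclusion assumes that no other document sets an order of precedence; the protocol does not refer to one.

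**What to change.** - Reconcile Dose Modification and the Safety Labs Schedule into one ordered rule for triglycerides > 200 mg/dL. State whether each step is mandatory or discretionary, and refer to that rule wherever else the threshold appears.
- Reconcile section G and the Safety Labs Schedule into one rule for bleeding. State which instruction applies when both triggers are met, and make section G's reference to dose modifications point to text that contains the rule.
- Align the withdrawal list and the Overdose text with the result.

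The sponsor's clinicians decide the content of each rule; this review takes no position on it. The cost is a wording amendment to the protocol, with no change to sample size, data collection or analysis.

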## RISKS AND DISCOMFORT

### Potential Risk of Omegaven® Treatment

Omegaven® has been studied in animal pre-clinical models as well as Phase I, II, III, and post marketing human trials in both Europe and Asia. Prolonged bleeding time and an inhibited platelet aggregation can occur. It should not be administered to patients known to be allergic to fish or egg protein.

### Contraindications to Omegaven® include the following:

Impaired lipid metabolism  
Severe hemorrhagic disorders  
Unstable diabetes mellitus  
Collapse and shock  
Stroke/Embolism  
Recent cardiac infarction  
Undefined coma status

[name], Department of Surgery, Children's Hospital & Medical Center  
[name], Department of Surgery, Children's Hospital & Medical Center  
[name], Pediatric Research Office, Dept. of Pediatrics, UNMC  
[name], Department of Biostatistics, College of Public Health, UNMC

**Side effects:**

The infusion of Omegaven® can lead to a prolonged bleeding time and an inhibited platelet aggregation. In rare cases, patients may experience a fishy taste.

The administration of Omegaven® should be stopped or reduced if there is a marked increase in blood glucose levels during the Omegaven® infusion. Undesirable effects that are seen during the infusion of Omegaven® that may also occur with conventional fat emulsions (i.e. Intralipid®) include:

Slight rise in body temperature  
Heat sensation and/or cold sensation  
Chills  
Flushing or cyanosis  
Lack of appetite, nausea, vomiting  
Dyspnea  
Headache, pain in the chest, bone pain  
Priapism  
Increase/decrease in blood pressure  
Anaphylactic reactions/erythema

Other expected adverse events that are common to all patients with short bowel syndrome, regardless of the type of fat emulsion they receive, include blood stream infections and re-admittance to hospital. Causes for re-hospitalization include dehydration, bloodstream infections, electrolyte abnormalities, bowel obstruction, and central venous catheter malfunction.

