#### Hypothesis for Aim 1:

1.1 – After starting Omegaven® on PN, the rate of fatty acid deficiencies and imbalances will be as low as before Omegaven®. Also, the rate of triglyceride events > 400 mg/dL with Omegaven® will be similar to that seen with PN administered with soy oil IFE (conventional emulsion, i.e., Intralipid®).

1.2 – PN containing Omegaven® will be safe for patients with respect to the risk of unexpected bleeding, coagulopathies, and other adverse events.

[name], Department of Surgery, Children's Hospital & Medical Center  
[name], Department of Surgery, Children's Hospital & Medical Center  
[name], Pediatric Research Office, Dept. of Pediatrics, UNMC  
[name], Department of Biostatistics, College of Public Health, UNMC

1.3 – PN containing Omegaven® will promote more short-term growth and development than conventional fat emulsions.

2. To determine if established PN associated liver disease can be reversed or its progression halted by using a parenteral fat emulsion prepared from fish oil as measured by normalization of serum levels of hepatic enzymes and bilirubin.

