### Outcome/Endpoints

#### *Treatment safety*

Our primary outcome for treatment safety will be based on patient's essential fatty acid profile. We will compare patients before treatment with Omegaven® started and after treatment started (one month after treatment started until treatment stopped) with respect to the frequency with which triene/tetraene ratio  $> 0.2$  at any time. Primary analyses for these and all other safety outcomes will be based on a follow-up time for Omegaven® starting 30 days after baseline, i.e., 30 days after treatment started for Omegaven® patients and 2 months after the first direct bilirubin level  $< 2$  mg/dL was recorded.

Additional comparisons across treatment periods for subjects receiving Omegaven® will be aimed to assess occurrence of spontaneous bleeding (e.g., unexplained bruising, oozing from gums/incision sites), and maximum triene/tetraene ratio, minimum platelets, maximum international normalized ratio (INR), and trends in pre-albumin (age standardized levels). We will also explore trends in coagulopathies based on curves of platelets, prothrombin time (PT), partial thromboplastin time (PTT) over time, and INR. We will also describe the rate with which INR ratios were  $> 2$  (number of days/follow-up time), as a marker of coagulopathies.

Additional evaluation of Omegaven® will be performed with regards to rate in which albumin is  $> 3$  g/dL, maximum triglyceride level, rate of blood stream infections (number of positive blood cultures/follow-up-time under PN after baseline), rate of central venous catheter (CVC) infections (number of CVC infections/follow-up time and number of gram positive CVC infections/follow-up time), and occurrence of anaphylactic reactions after baseline.

We will describe trends over time for all outcomes associated with fatty acid profiles (including triene/tetraene ratios, triglycerides, total omega-6 fatty acids, total omega-3 fatty acids, total saturated, total monounsaturated, and total polysaturated fatty acids). Specific fatty acids such as arachidonic, palmoleic, palmitic, oleic, stearic, and linoleic fatty acids will also be evaluated and described.

[name], Department of Surgery, Children's Hospital & Medical Center  
[name], Department of Surgery, Children's Hospital & Medical Center  
[name], Pediatric Research Office, Dept. of Pediatrics, UNMC  
[name], Department of Biostatistics, College of Public Health, UNMC

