### *Analysis of Safety and Tolerability of Omegaven®*

All primary safety and tolerability analyses will be based on descriptive statistics. In secondary analyses, we will also assess the statistical significance of differences. The period receiving Omegaven® will start 30 days after beginning PN with Omegaven® for the main analysis. Outcomes measured in the Omegaven® will be described for a period starting 30 days after baseline.

Primary outcomes measured will include whether the triene/tetraene ratio was ever  $> 0.2$  during the intervention period and whether the INR was ever  $> 2$ . Secondary outcomes measured will include platelets, prothrombin time (PT), partial thromboplastin time (PTT), and other components of the fatty acid profile. Analysis of all categorical outcomes will be based on proportions and of all continuous outcomes will be based on means or medians of the individual mean, maximum or minimum values, as appropriate, during the respective follow-up period. Comparisons between periods (pre and post-treatment) will be performed based on paired tests, parametric or non-parametric, as appropriate. We will also explore trends over time (e.g., decreasing for INR and increasing for pre-albumin) and estimate p-values via regression models using generalized estimating equations or random effects to account for within subject correlations. When describing outcomes over time, we will explore the effect of predictors of poor hepatic outcomes, such as use of antifungal agents (e.g., amphotericin) and antidiarrheal agents (e.g., loperamide), on potential spikes.

[name], Department of Surgery, Children's Hospital & Medical Center  
[name], Department of Surgery, Children's Hospital & Medical Center  
[name], Pediatric Research Office, Dept. of Pediatrics, UNMC  
[name], Department of Biostatistics, College of Public Health, UNMC

We will also evaluate nutritional outcomes including difference in weight-for- age Z-scores and height-for-age Z-scores from baseline to the moment in which the child starts enteral feeding and to the moment in which the child receives less than 10% of their calories from PN. Using linear regression, we will explore adjustment for baseline alternative predictors of interest. Trends over time in Z-scores will also be explored using regression with repeated measure methods.

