**Summary – Overall Risk Assessment**

Patients will be at some risk inherent in taking a pharmaceutical agent that has not been fully evaluated for long duration treatment. However, the availability of safety data demonstrates no life-threatening risks or toxicities to vital organs or physiologic functions. Prolonged bleeding times and inhibition of platelet aggregation are a potential risk, especially to those patients with an underlying coagulopathy or those being treated with an anticoagulant. The potential benefits

[name], Department of Surgery, Children's Hospital & Medical Center  
[name], Department of Surgery, Children's Hospital & Medical Center  
[name], Pediatric Research Office, Dept. of Pediatrics, UNMC  
[name], Department of Biostatistics, College of Public Health, UNMC

of Omegaven® in this patient population are mainly based on the experimental evidence. However, the study will only be available to those for whom no standard therapy is available or appropriate, or has already failed. The risks and potential benefits will require careful individual assessment by both the investigators and patients. The heterogeneity of clinical manifestations will lead to non-uniform risk-benefit ratios across the eligible patient population.

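### Spontaneous bleeding, the one outcome that would register the platelet-function hazard the protocol names, is not a primary safety outcome, and its main analysis leaves out the first 30 days on treatment

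*Protocol*

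**What the plan says.** **The hazard.** The protocol describes the bleeding risk in three places, each time as the same two effects.

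- Side effects: "The infusion of Omegaven® can lead to a prolonged bleeding time and an inhibited platelet aggregation".
- Potential Risk of Omegaven® Treatment: "Prolonged bleeding time and an inhibited platelet aggregation can occur".
- Summary – Overall Risk Assessment: "Prolonged bleeding times and inhibition of platelet aggregation are a potential risk, especially to those patients with an underlying coagulopathy".

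**The hypothesis.** Hypothesis 1.2 reads: "PN containing Omegaven® will be safe for patients with respect to the risk of unexpected bleeding, coagulopathies, and other adverse events". Bleeding and coagulopathy are separate items in it.

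**The outcomes, Treatment safety section.** The primary safety outcome here is the essential fatty acid profile (triene/tetraene ratio above 0.2). Among the further before-and-after comparisons, the plan will "assess occurrence of spontaneous bleeding (e.g., unexplained bruising, oozing from gums/incision sites"). Minimum platelets and maximum INR stand in the same list. The section adds: "We will also explore trends in coagulopathies based on curves of platelets, prothrombin time (PT), partial thromboplastin time (PTT) over time, and INR". It treats the rate of INR above 2 as an indicator of coagulopathy. The primary analyses of all safety outcomes start 30 days after baseline.

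**The outcomes, Analysis of Safety and Tolerability section.** There are now two primary outcomes: triene/tetraene ratio ever above 0.2 and INR ever above 2. Platelets, PT, PTT and the rest of the fatty acid profile are secondary. Spontaneous bleeding is not named. The main analysis again starts 30 days after treatment begins. On trends, the section says: "We will also explore trends over time (e.g., decreasing for INR and increasing for pre-albumin").

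**The concern.** The two outcome sections rank the haemostasis outcomes differently. In Treatment safety, INR and spontaneous bleeding both sit below the fatty acid profile. In the analysis section INR rises to primary status and spontaneous bleeding drops out of the named outcomes. The outcome that was raised does not measure the hazard in the risk sections, and the one that was dropped would.

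INR can also move for a reason unrelated to platelets. The children enrolled have liver disease, and the plan gives a falling INR as an example of a trend to explore. That is the direction expected if the liver recovers. The main haemostasis result could therefore improve while a platelet-mediated bleeding effect is present.

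The 30-day start adds to this. It may suit a fatty acid profile that needs time to change, but applied to bleeding it removes the first month of exposure from the main result. At stake is whether the trial's headline safety result can answer the bleeding part of hypothesis 1.2.

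**Working it through.** **Step 1. Match each planned measure to the named hazard.**

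| Measure | What it reflects | Registers a platelet-function effect? | Rank in Treatment safety | Rank in the analysis section |
|---|---|---|---|---|
| INR above 2 | Clotting factors | No | Below primary | Primary |
| PT, PTT | Clotting factors | No | Below primary | Secondary |
| Platelet count | Number, not function | No | Below primary | Secondary |
| Spontaneous bleeding | Clinical bleeding by any mechanism | Yes, if it leads to bleeding | Below primary | Not named |

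The Reversal Study Lab Schedule, the Safety Labs Schedule and Tables 2 and 3 contain no bleeding-time or platelet-aggregation test. Fibrinogen is drawn, but it is a monitoring test and not a named outcome.

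**Step 2. What the bleeding outcome can show at the protocol's sizes.** The inputs are n = 20, 25 or 30 (Statistical Power and Sample Considerations). The protocol gives no bleeding risk, so 5% and 10% are assumptions. All n children are taken to be observed over the whole counting window, independently and with the same risk.

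The upper one-sided 95% limit with zero affected children is 1 − 0.05^(1/n):

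- n = 20: 1 − 0.861 = 13.9%
- n = 25: 1 − 0.887 = 11.3%
- n = 30: 1 − 0.905 = 9.5%

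The upper end of a two-sided 95% exact interval with zero affected is 1 − 0.025^(1/n): 16.8%, 13.7% and 11.6%.

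The chance of at least one affected child is 1 − (1 − p)^n:

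| Assumed risk p | n = 20 | n = 25 | n = 30 |
|---|---|---|---|
| 5% | 1 − 0.358 = 64% | 1 − 0.277 = 72% | 1 − 0.215 = 79% |
| 10% | 1 − 0.122 = 88% | 1 − 0.072 = 93% | 1 − 0.042 = 96% |

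**Step 3. Effect of the 30-day start.** The protocol does not say how bleeding risk is spread over time, so the loss can lie anywhere between none and all of it. As an illustration, suppose the total risk is 10% and half the affected children bleed only in the first 30 days. The main analysis then sees a risk of 5%, and the chance of recording any affected child falls from 88% to 64% at n = 20, and from 96% to 79% at n = 30.

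The protocol has no figure of its own on bleeding to reproduce. Table 4 gives McNemar power for general differences in adverse-event frequency and does not bear on this point.

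**The case against.** The strongest reply is that the protocol does not make the inference a reader might draw. Three stronger readings are tempting, and the text supports none of them.

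- *That INR is offered as proof of bleeding safety.* It is not. Hypothesis 1.2 lists bleeding and coagulopathy separately, the Treatment safety section gives each its own outcome, and INR above 2 is tied to coagulopathy. INR is a proper measure of that part of the hypothesis. It has some bearing on the named risk too, since the overall risk summary says that risk is greater in children with an underlying coagulopathy.
- *That bleeding is not measured.* It is, as spontaneous bleeding.
- *That early bleeds would be missed.* Adverse events are assessed from the first infusion, the investigators review cases at least monthly, evidence of bleeding is a listed trigger for dose reduction, and the DSMB chair receives all adverse event reports. The 30-day start affects the main analysis, not surveillance.

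It can also be said that the primary safety analyses are descriptive, that no decision rule hangs on the primary label, and that the list in the analysis section is worded as inclusive, so bleeding is not expressly shut out. All of that stands, and it limits the weight of the point.

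It does not remove the point. The label and window still decide which bleeds appear in the main safety result, and the analysis section names INR and leaves out bleeding. A before-and-after comparison of bleeding could itself be affected by liver recovery, so raising its rank does not cure confounding.

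**Conclusion.** The point holds as a fault of ranking and counting window. The hazard named three times is a platelet-function effect. The only primary haemostasis outcome does not measure platelet function. The outcome that would register the hazard is ranked below primary in one section, unnamed in the other, and analysed in the main from day 30 only.

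The gain from correcting this is real but modest. With 20 to 30 children, a finding of no bleeding would still be compatible with a risk of roughly 10% to 14% (one-sided 95%), so it would exclude only fairly common bleeding. These figures rest on the assumptions in the working, namely complete observation and equal, independent risks. The share of bleeds lost to the 30-day start cannot be estimated from the protocol.

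**What to change.** Reconcile the Treatment safety section with the Analysis of Safety and Tolerability section:

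1. Name spontaneous bleeding as a primary safety outcome in both, counted from the first infusion. Exempt it from the 30-day start, which can remain for the fatty acid outcomes.
2. Report the number of children affected and the number of events, with an exact confidence interval for the proportion of children affected.
3. Keep INR, PT, PTT and platelet count as coagulopathy measures. State that INR results will be read as evidence on coagulopathy only, and not on the bleeding-time or platelet-aggregation risk.

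The cost is wording. No assay, blood draw or change in patient care is involved, and adverse events are already collected from the first infusion. The downside is that clinical bleeding is rarer and more subjective than INR, so the interval will be wide. Any before-and-after comparison should carry the caveat that liver recovery may affect it.
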